9.3 Secondary End Point

Table 11 Proportion of patients experienced major bleeding

		Day 1	Day 8	Day 15	p-value
Assessment of Bleeding:	Normal, N (%)				
	Abnormal, N (%)				
Type Of Blood Transfusions:	Whole Blood, N (%)				
	RBCs, N (%)				
	Platelets, N (%)				
	Plasma, N (%)				

Table 12 *Number and percent of Adverse Event among treatment groups*

	N = 100	p-value
Total No of AE, N (%)		
AE1, N (%)		
AE2, N (%)		
AE3, N (%)		

Table 13 *Number and percent of Serious Adverse Event among treatment groups*

	N = 100	p-value
Total No of SAE, N (%)		
SAE1, N (%)		
SAE2, N (%)		
SAE3, N (%)		

Table 14 *Percent Change in mean Hb%*

	Screening	Day 1	Day 8	Day 15	p-value
Hb%, (mean ± SD)					
% change					
p-value					

Table 15 *Percent Change in mean Platelets count*

	Screening	Day 1	Day 8	Day 15	p-value
Platelets count, (mean ± SD), x 10³/μL					
% change					
p-value					

Table 16 *Percent Change in mean Systolic BP*

	Screening	Day 0	Day 1	Day 8	Day 15	p-value
Systolic BP, (mean ± SD), mmHg						
% change						
p-value						

Table 17 *Percent Change in mean Diastolic BP*

	Screening	Day 0	Day 1	Day 8	Day 15	p-value
Diastolic BP, (mean ± SD), mmHg						
% change						
p-value						

Table 18 *Percent Change in mean Sitting Pulse Rate*

	Screening	Day 0	Day 1	Day 8	Day 15	p-value
Sitting Pulse Rate, (mean ± SD), beats /min						
% change						
p-value						

Table 19 *Percent Change in mean Oral Temperature*

	Screening	Day 0	Day 1	Day 8	Day 15	p-value
Oral Temperature, (mean ± SD), °C						
% change						
p-value						

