6.2. The operative Phase

During this phase, patient's registries for the type of surgery done, Type of anesthesia, patient position and type of prosthesis, & blood transfusion during surgery should be recorded. And IMP dispensing 6 hours after surgery or upon adequate hemostasis will be done. APTT will be done 4 & 8 hours after the first dose

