16.1. Adverse Events Monitoring

All AEs regardless of seriousness or relationship to IMP, spanning from the signature of the informed consent form, until the end of the study as defined by the protocol for that patient, are to be recorded on the corresponding page(s) included in the CRF and reported as described in the following sections.

For all adverse events, the investigator must pursue and obtain information adequate both to determine the outcome of the adverse event and to assess whether it meets the criteria for classification as a serious adverse event requiring immediate notification to Sponsor or its designated representative.

For all adverse events, sufficient information should be obtained by the investigator to determine the causality of the adverse event. The investigator is required to assess causality. For adverse events with a causal relationship to the investigational product, follow-up by the investigator is required until the event or its sequelae resolve or stabilize at a level acceptable to the investigator, and Sponsor concurs with that assessment. This may imply that observations will continue beyond the last planned visit per protocol, and that additional investigations may be requested by the Monitoring Team up to as noticed by the sponsor

Whenever possible, diagnosis or single syndrome should be reported instead of symptoms. The Investigator should specify the date of onset, intensity, action taken with respect to IMP, corrective treatment/therapy given, additional investigations performed, outcome and his/her opinion as to whether there is a reasonable possibility that the AE was caused by the IMP.

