1.2 Study Rationale

The purpose of this study is to conduct several investigations required to evaluate the efficacy and safety of subcutaneous Thrombexx ampoules in the prophylaxis of Deep Vein Thrombosis (DVT) post major orthopedic operations

2 Study Design

A Prospective, Single- Center, Phase IV Interventional, Single Arm conducted in Egypt to assess the efficacy and safety of patients undergoing major orthopedic operations such as Total knee & hip Arthroplasty with complete data and who had 2 weeks follow-up.

This study will be conducted through main phases, preoperative phase which will be as a screening visit, operative phase which is the surgery will be done and a total of 3 follow-up visits which is the postoperative phase.

1. Pre-operative phase
2. Operative phase
3. Post-operative phase (follow-up)

Detailed descriptions of the study design are as follows:

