9.4 Study Discontinuation

Table 20 Number and percent of causes of treatment discontinuations

		N = 100	p-value
Did the patient complete the study as per protocol?	Yes, N (%)		
	No, N (%)		
Reason for the discontinuation from study	Patient Withdrew Voluntarily		
	Adverse Event		
	Lost Follow-up		
	Death		
	Other Reasons		

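### SAP Tables 12 and 13 set an event total over 100 patients, ask for p-values in a one-arm trial, and do not separate events before the first dose

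*SAP*

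**What the plan says.** SAP section 2 describes the trial as "A Prospective, Single- Center, Phase IV Interventional, Single Arm conducted in Egypt". Section 4.2 makes the number of reported AEs or SAEs a secondary endpoint. Section 8.2.2 repeats it as a number of events, next to major bleeding as a proportion of patients. For categorical variables, section 8.2.3 prescribes frequency, percentage and a 95% confidence interval. It sets a two-sided 0.05 level but names no test.

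The table shells are in SAP section 9.3. Table 12 is titled "Number and percent of Adverse Event among treatment groups" and Table 13 "Number and percent of Serious Adverse Event among treatment groups". Each has one column headed N = 100 and a p-value column. The top rows read "Total No of AE, N" and "Total No of SAE, N", each followed by a percent sign in brackets. The rows below (AE1 to AE3, SAE1 to SAE3) are also N (%). Neither table shows a confidence interval or a time window. Table 20 in section 9.4, "Number and percent of causes of treatment discontinuations", likewise has one N = 100 column and a p-value column.

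On timing, Protocol 16.1 records all AEs over a period "spanning from the signature of the informed consent form" to the end of the study, whatever their relation to the drug. The flow chart in Protocol 7.1 starts the AE row on Day 0. Protocol 6.2 gives the general dosing rule: "IMP dispensing 6 hours after surgery or upon adequate hemostasis will be done". For spinal anesthesia, Protocol 12.1 also describes a dose 8 to 10 hours before puncture. Neither document defines a treatment-emergent event.

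**The concern.** Three features of these shells do not fit the trial.

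- **Unit.** A number of events over a number of patients is not a proportion. Several events per patient are plausible: Protocol 16.3 counts abnormal test findings as AEs, and APTT alone is measured at six timepoints.
- **P-values.** With one group and no reference rate there is nothing to compare. The shells ask for a p-value and omit the confidence interval that section 8.2.3 calls for.
- **Time window.** Collection starts at consent, so events of the operation enter the same rows as events after dosing. The transfusion criterion for major bleeding excludes the perioperative period (Protocol 8.2); the AE endpoint has no such separation. With no control arm, nothing in the data can show how much of the total is surgical background.

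At stake is whether the AE percentages can be read as the share of patients who had an event on the drug. As drafted they cannot.

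**Working it through.** **The plan's own figure.** The documents give no AE rate, so there is none to reproduce. The only computed figure is the sample size of 168: n = z²p(1−p)/d² = 1.96² × 0.125 × 0.875 / 0.05² = 168.1. It reproduces but does not feed these tables. Every rate below is an assumption chosen to show a range.

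**1. Event total against patients affected.** Inputs: denominator 100 (Tables 12 and 13); assume 30 patients have at least one AE. The patient-level figure is 30/100 = 30%, exact (Clopper-Pearson) 95% CI 21.2% to 40.0%. The total row would print 30 × k / 100, where k is events per affected patient:

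| k | Events | Printed | Patients affected |
|---|---|---|---|
| 1 | 30 | 30% | 30% |
| 1.5 | 45 | 45% | 30% |
| 2 | 60 | 60% | 30% |
| 4 | 120 | 120% | 30% |

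A binomial interval computed on 60 of 100 would be 49.7% to 69.7%, which excludes the 30% of patients affected. On 120 of 100 no binomial interval exists.

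The gap depends on how common events are. If events per patient follow a Poisson distribution with mean m, the row prints 100m% and the share of patients affected is 1 − exp(−m):

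| m | Printed | Patients affected |
|---|---|---|
| 0.2 | 20% | 18.1% |
| 0.5 | 50% | 39.3% |
| 1.0 | 100% | 63.2% |
| 1.5 | 150% | 77.7% |

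**2. P-values.** A contingency table with one column has (1 − 1) × (rows − 1) = 0 degrees of freedom, so it contains no contrast. A one-sample test would need a null value, and none is stated. Tables 8 to 11 and 14 to 19 have several timepoints, so a within-patient comparison is at least conceivable there. Tables 12, 13 and 20 have a single column.

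**3. Pre-dose events.** Keep 30 affected patients and let a share s of them have only pre-dose events. Post-dose incidence is 30(1 − s)/100:

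| s | Patients with a post-dose event | Exact 95% CI |
|---|---|---|
| 0% | 30% | 21.2% to 40.0% |
| 10% | 27% | 18.6% to 36.8% |
| 20% | 24% | 16.0% to 33.6% |
| 30% | 21% | 13.5% to 30.3% |
| 50% | 15% | 8.6% to 23.5% |

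Protocol 16.1 asks for the date of onset, not the time. Surgery and first dose can both fall on Day 0, and then the date alone cannot place an event before or after the first dose.

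**The case against.** The strongest reply is that the endpoint is defined as a count of all AEs and SAEs during the study, so a count from consent onward is exactly what was promised. That stands. A reader might infer that the safety endpoint itself will be misstated; the documents do not support this. Nothing in them calls the total a drug-related rate, and Protocol 16.1 separately requires a causality assessment for each event, though Tables 12 and 13 do not tabulate it. The safety objective is framed in terms of serious bleeding, which is reported in Table 11 and is not touched by this point.

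Three other strong readings also fail:

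- **That every intra-operative event is pre-dose.** Protocol 12.1 describes a dose before puncture under spinal anesthesia, Protocol 6.1 leaves the regimen to the investigator within the label, and Protocol 4.1 describes a labelled dose shortly before surgery. The overstatement can be argued only for patients first dosed after surgery.
- **That every row divides events by patients.** Only the total rows are worded as events. AE1 to AE3 and SAE1 to SAE3 share the layout of the medical history and medication tables and may be patient counts; the SAP does not say.
- **That the distortion is large.** No event rate is given, and at 0.2 events per patient it is about two percentage points.

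It can also be said that the p-value columns are template leftovers. That is likely, but it is a reason to delete them. The tables also state no time window, so the inclusion of pre-dose events is inferred from Protocol 16.1 and the flow chart.

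**Conclusion.** The point holds in limited form. Followed as drafted, the total rows of Tables 12 and 13 give a percentage that is not a proportion, can exceed 100% and cannot carry the planned 95% confidence interval. The p-values in Tables 12, 13 and 20 have no defined meaning. The raw event count remains valid as the stated endpoint. Incidence on the drug may be overstated for patients first dosed after surgery, because pre-dose events are not separated.

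The size cannot be fixed from the documents. On the assumed rates it runs from 20% printed against 18.1% affected when events are rare, to 120% printed against 30% affected when each affected patient has four events. The pre-dose effect ranges from none to a halving, depending on the assumed share of patients with pre-dose events only. The point should be corrected before the data are collected, since the onset time on Day 0 may not be recoverable later.

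**What to change.** - In Tables 12 and 13, keep the total number of events without a percentage. Add patients with at least one AE (or SAE) with onset after the actual first dose, as n over all treated patients with an exact 95% CI. State that AE1 to AE3 and SAE1 to SAE3 count patients.
- List events between consent and first dose separately.
- Delete the p-value columns in Tables 12, 13 and 20, and the reference to treatment groups in the titles of Tables 12 and 13.
- Align the AE row of the flow chart (Protocol 7.1) with Protocol 16.1.
- Reconcile the first-dose timing in Protocol 12.1 with Protocol 6.2 and SAP 2.2. Classifying by the actual time of first dose works whichever way that is settled.
- Record onset time as well as date for events on Day 0.

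The cost is edits to the table shells, one CRF field, and a minor protocol edit for the flow chart. Because the event count is kept, the patient-level figure is an added summary and does not replace the endpoint. Replacing the count outright would change the endpoint and call for an amendment under Protocol 15.2.

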Statistical analysis	
- Descriptive analysis: All statistical tests used a significance level of P=0.05, two tailed tests are performed for all analyses used statistical testing. Descriptive analysis for quantitative data will include count, mean with 95% CI, standard deviation, median, minimum and maximum. For qualitative categorical variables; frequency and percentage and 95% confidence interval will be applied.

Stopping rules	
DVT PE Major bleeding Allergy APTT value increases by 2-2.5 folds According to investigator evaluation

Table of Contents

Title Page	1
1. Synopsis	2
Table of Contents	6
2. LIST OF ABBREVIATIONS	9
3. SIGNATURE(S) PAGE	10
4. INTRODUCTION	11
4.1. Background	11
4.2. Correlative studies:	11
4.3. Study Rationale	12
5. STUDY OBJECTIVES	12
5.1. Primary Objectives	12
5.2. Secondary objectives	12
6. TRIAL DESIGN	12
6.1. The pre-operative Phase	12
6.2. The operative Phase	13
6.3. The Follow-up Phase	13
7. FLOW CHARTS:	13
7.1. STUDY FLOW CHARTS:	13
7.2. STUDY PHASES	14
8. STUDY OUTCOME MEASURES	15
8.1. Primary Endpoints	15
8.2. Secondary Endpoints	16
9. STUDY POPULATION	16
9.1. Recruitment strategy:	16
9.2. Inclusion Criteria	16
9.3. Exclusion Criteria	16
10. STUDY PROCEDURE:	17
10.1. Selection of the study population:	17
10.2. Case Report Form	17
11. SOURCE DATA	17

12.	TREATMENT OF TRIAL PARTICIPANTS	18
12.1.	Description of Study Medication(s)	18
12.2.	Concomitant Medication (if applicable).....	19
13.	DATA COLLECTION	19
15.1.	DATA MANAGEMENT	20
15.2.	AMENDMENT TO THE PROTOCOL.....	20
15.2.1.	Protocol Deviations	20
15.2.2.	Onsite Audits.....	20
15.2.3.	Study Monitoring	21
15.3.	PREMATURE DISCONTINUATION OF STUDY.....	22
16.	SAFETY REPORTING AND DEFINITIONS	22
16.1.	Adverse Events Monitoring.....	22
16.2.	Reporting Period.....	23
16.3.	Adverse Event (AE):	23
16.4.	Serious Adverse Events	24
16.4.1.	Instructions for Reporting Serious Adverse Events	24
17.	STATISTICAL METHODOLOGY	24
17.1.	Determination of Sample Size.....	24
17.2.	Analysis Variables:.....	25
17.2.1.	Primary analysis variables:.....	25
17.2.2.	Secondary analysis variables:.....	25
17.2.3.	Statistical Method:.....	25
17.2.4.	Interim Analysis	25
18.	ETHICS.....	25
18.1.	INDEPENDENT ETHICS COMMITTEE (IEC) OR INSTITIUTIONAL REVIEW BOARD (IRB).....	25
18.2.	Ethical principles:	26
18.3.	Laws and regulations:	26
18.4.	PATIENT INFORMATION AND CONSENT	26
18.5.	DISCONTINUATION OF THE STUDY	27
18.5.1.	PREMATURE DISCONTINUATION OF STUDY	27

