8. STUDY OUTCOME MEASURES

8.1. Primary Endpoints

Primary end points included new onset symptomatic thrombosis requiring medical or surgical intervention or death due to thrombosis defined as fatal PE, ischemic

Sponsor: Minapharm Pharmaceuticals
Protocol Number: Sub-Thromb-001
Version: 1 amendment 1

stroke, mesenteric thrombosis, or myocardial infarction.

The number of clinical PE events will be measured by spiral CT

Mean changes in APTT where it will be done before first dose, 4 & 8 hours after first dose then on days 1,8,15 post operatively

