2.3 The Follow-Up Phase

During this phase which is approximately 15 days, PE (Pulmonary Embolism) which is confirmed by spiral CT chest, any new DVT appears also to be confirmed by Doppler ultrasound, Bleeding assessment, APTT will be done on days 1, 8 & 15, concomitant medications, Hospital stay and any adverse event data will all be recorded

3 Study Objective:

3.1 Primary Objectives:

- To evaluate the efficacy of Subcutaneous Thrombexx® ampoules (r-Hirudin RB variant 15 mg) in DVT prophylaxis post major orthopedic operations

3.2 Secondary Objectives:

- To evaluate the safety of Subcutaneous Thrombexx® ampoules (r-Hirudin RB variant 15 mg) in DVT prophylaxis post major orthopedic operations in terms of serious bleeding.
- Predictive factors; baseline characteristics, Thrombexx® dose, duration and concomitant medications.
- Study population demographics and characteristics.

4 Study Outcome Measures:

4.1 Primary Endpoints:

- Primary end points included new onset symptomatic thrombosis requiring medical or surgical intervention or death due to thrombosis defined as fatal PE, ischemic stroke, mesenteric thrombosis, or myocardial infarction.
- The number of clinical PE events will be measured by spiral CT
- Mean changes in APTT where it will be done before first dose, 4 & 8 hours after first dose then on days 1,8,15 post operatively

4.2 Secondary Endpoints:

- **Major Bleeding:** was defined as clinically evident hemorrhage associated with a hemoglobin decrease ≥ 2 g/dL that leads to a transfusion of ≥ 2 units of whole blood or packed red cells outside of the perioperative period (time from the start of the surgery or procedure and up to 12 hours after), or hemorrhage that is intracranial, retroperitoneal, or into a prosthetic joint.

- Number of any reported (AE) or (SAE) during the study duration.

5 Study Population

This is a prospective study, it is important to have a well-defined study population in place prior to the start of the study. Study populations should be defined using specific inclusion and exclusion criteria, which will be used to evaluate a potential subject's ability to participate in the study.

5.1 Recruitment strategy:

It is essential that the recruitment process take into account factors that will optimize the type and number of participants enrolled in the study while minimizing time and expense. Failure to meet target accrual goals can affect the "power" of a study, making it less successful in providing quality results.

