9.2 Primary End Point

Table 8 *Proportion of patients experienced new onset symptomatic thrombosis*

		Follow-up 1 (Day 1)	Follow-up 2 (Day 8)	Follow-up 3/ End of Study (Day 15)	p-value
Was a Routine bilateral compression Doppler done?	Yes, N (%)				
	No, N (%)				
If “No”, please indicate a reason	Reason 1, N (%)				
	Reason 2, N (%)				
	Reason 3, N (%)				
Is the report interpreted, signed & dated by the PI or any of the designated site staff?	(Yes), N (%)				
	(No), N (%)				
If “No”, please indicate a reason:	Reason 1, N (%)				
	Reason 2, N (%)				
	Reason 3, N (%)				
If “Yes”, the report interpretation shows that the subject is:	Normal, N (%)				
	Abnormal, N (%)				
If abnormal, please state the reason:	Reason 1, N (%)				
	Reason 2, N (%)				
	Reason 3, N (%)				

Table 9 *The number of clinical PE (Pulmonary Embolism) events will be measured by spiral CT*

		Follow-up 1 (Day 1)	Follow-up 2 (Day 8)	Follow-up 3/ End of Study (Day 15)	p-value
Was a Spiral CT done?	Yes, N (%)				
	No, N (%)				
If “No”, please indicate a reason	Reason 1, N (%)				
	Reason 2, N (%)				
	Reason 3, N (%)				
Is the report interpreted, signed & dated by the PI or any of the designated site staff?	(Yes), N (%)				
	(No), N (%)				
If “No”, please indicate a reason:	Reason 1, N (%)				
	Reason 2, N (%)				
	Reason 3, N (%)				
If “Yes”, the report interpretation shows that the subject is:	Normal, N (%)				
	Abnormal, N (%)				
If abnormal, please state the reason:	Reason 1, N (%)				
	Reason 2, N (%)				
	Reason 3, N (%)				

Table 10 *Mean changes in Activated Partial Thromboplastin Time (APTT) where it will be done before first dose, 4 & 8 hours after first dose then on days 1,8,15 post operatively*

		Before 1 st dose	After 1 st dose		Post-operative			p- value
			4 h	8 h	Day 1	Day 8	Day 15	
Was an APTT test performed?	Yes, N (%)							
	No, N (%)							
If “No”, please indicate a reason	Reason 1, N (%)							
	Reason 2, N (%)							
	Reason 3, N (%)							
If “Yes”, the test result is	APTT; Mean ± SD (sec)							
APTT, % change								
p-value								
The test interpretation shows that the subject is:	Normal, N (%)							
	Abnormal, N (%)							
If abnormal, please state the reason:	Reason 1, N (%)							
	Reason 2, N (%)							
	Reason 3, N (%)							

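### Tables 14-19 report percent change of visit means, and Table 10 has no mean-change row for the APTT endpoint; neither gives paired n, SD or CI for the change

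*SAP*

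**What the plan says.** **Tables 14 to 19 (SAP 9.3).** The titles run from "Percent Change in mean Hb" to "Percent Change in mean Oral Temperature", covering hemoglobin, platelets, systolic and diastolic pressure, pulse and temperature. Each shell has a row of visit mean ± SD, one row for percent change and p-value cells. No shell has a per-visit count, a within-patient change, or a measure of spread for the change.

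**Table 10 (SAP 9.2).** Its title begins "Mean changes in Activated Partial Thromboplastin Time (APTT) where it will be done before first dose". The rows give mean ± SD in seconds at each time point, a percent change that is not defined, and p-values. Unlike Tables 14 to 19, it records at each time point whether the test was done ("Was an APTT test performed"), with reasons if not. There is no row for change in seconds.

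**The endpoint.** Protocol 8.1 lists "Mean changes in APTT where it will be done before first dose" among the primary endpoints, and SAP 4.1 repeats it.

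**The method.** SAP 8.2.3 asks, for quantitative data, for count, mean with 95% CI, SD, median, minimum and maximum. It does not define change, name a test or give a rule for missing values.

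**The concern.** A change from baseline is something that happens to a patient. A percent change of visit means is a comparison of two groups, and they are the same group only if everyone measured at baseline is measured later. Without a paired count, the reader of Tables 14 to 19 cannot tell a change in patients from a change in who was measured. Without an SD or CI for the change, the reader cannot judge its precision either.

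For APTT the gap is plainer: the listed endpoint is a mean change, and its own table does not report one. Two programmers could also fill the percent-change row differently, one from the means and one from each patient's own percentage, and print different figures.

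Temperature has a further problem. Zero on the Celsius scale is arbitrary, so a percent change depends on the unit chosen.

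**Working it through.** The plan states no figure on this point. The inputs below are assumptions, because the documents give no dropout rate and no means, SDs or correlations for these variables.

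**1. Precision of the change cannot be recovered from visit SDs.**
Var(change) = s₀² + s₁² − 2·r·s₀·s₁, where r is the within-patient correlation. Assume s₀ = s₁ = 6 s and n = 100.
- r = 0.3: SD of change = 6·√(2 × 0.7) = 7.10 s; half-width = 1.96 × 7.10/10 = 1.39 s.
- r = 0.8: SD of change = 6·√(2 × 0.2) = 3.79 s; half-width = 1.96 × 3.79/10 = 0.74 s (about 0.75 s with the t quantile).

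The same printed SDs are compatible with intervals that differ nearly twofold in width.

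**2. The percent-change row has two readings.**
This was simulated for APTT with complete data, baseline mean 30 s, a true 1.4-fold rise, baseline CV 10% to 20% and correlation 0.3 to 0.6.
- Percent change of the means: 40.0%.
- Mean of the patients' own percent changes: 40.6% to 44.5%.
- Absolute change: 12.0 s on either calculation. With complete data, the difference of means equals the mean difference.

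**3. Missing patients can create a change in the means.**
Let a fraction q have no later value. Let their baseline differ by D from the baseline mean b of those who stay, and let nobody change. Then
percent change of means = b/(b + qD) − 1, while the paired change is 0.

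Hemoglobin, b = 13 g/dL, D = −2 g/dL:

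| q | Baseline mean, all | Later mean | Percent change of means |
|---|---|---|---|
| 0% | 13.0 | 13.0 | 0 |
| 5% | 12.9 | 13.0 | +0.8% |
| 10% | 12.8 | 13.0 | +1.6% |
| 20% | 12.6 | 13.0 | +3.2% |

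With D = −1 g/dL the range for 5% to 20% is +0.4% to +1.6%. For platelets with b = 250 and D = −100 (×10³/µL) it is +2.0% to +8.7%. If D is positive the sign reverses. If D or q is zero there is no artefact.

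**4. Later values can be expected to be missing.**
Protocol 12.2 withdraws participants who need a treatment listed in the exclusion criteria. SAP Table 20 counts discontinuation by voluntary withdrawal, adverse event, loss to follow-up and death. Table 10 has rows for tests not done.

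**5. Temperature.**
A rise from 37 to 38 °C is 1/37 = 2.7%. The same rise in Fahrenheit is 1.8/98.6 = 1.8%.

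**The case against.** **Table 10 is not stated to use group means.** Correct. Its percent change is undefined and could be per patient, and its test-done rows make a changing denominator visible. The criticism of Table 10 is therefore only that the mean change, with SD and CI, is absent and the percent change undefined.

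**SAP 2 describes patients with complete data and two weeks of follow-up.** Used as a filter, this would put the same patients at every visit and remove the artefact in step 3. But Table 20 and the not-done rows of Table 10 foresee missing values, and complete data would still leave the change without an SD or CI.

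**The shells are abbreviated throughout.** Tables 1 and 6 also show only mean ± SD, so the missing CI is partly a general mismatch with SAP 8.2.3. That is fair. For a baseline table, however, the CI of a mean follows from SD and n. For a change it does not (step 1).

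**The variables are of limited weight.** Changes in hemoglobin, platelets and vital signs are not listed endpoints. APTT change is a primary endpoint in Protocol 8.1 and SAP 4.1, but it is not among the primary analysis variables in SAP 8.2.1. This lowers the weight of Tables 14 to 19, and leaves the listed APTT endpoint without its estimate.

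**A stronger reading that does not hold.** A reader might infer that the stopping rules take patients off and so make APTT appear to fall, and that paired change would correct this. The documents do not establish the first step. The synopsis lists "APTT value increases by 2-2.5 folds" as a stopping rule, but Protocol 15.3 and 18.5.1 give such criteria as reasons to end the trial, and no text says that a patient's measurements then cease. The second step is wrong. Suppose all patients share one baseline, 90 of 100 reach and hold 1.4-fold, and 10 reach 2.5-fold on Day 1 and have no later value. Day 1 shows 0.9 × 40% + 0.1 × 150% = +51%, and Day 8 shows +40%, by group means and by paired change alike. Paired change removes the baseline-mix artefact only.

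**Conclusion.** The point stands in a limited form and should be corrected. Three parts need no assumption:
- Tables 14 to 19 are, by title, percent changes of visit means, with no paired n and no SD or CI for the change.
- Table 10 does not report the mean change that its title and the listed endpoint name.
- A percent change of temperature depends on the unit.

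A spurious change in the means is a possibility, not a prediction. It needs missing later values and a baseline difference in those who are missing, and its direction depends on who they are. On the assumed inputs it is +0.8% to +3.2% for hemoglobin with 5% to 20% leaving. The documents do not support a claim that the tables will favour the drug.

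**What to change.** - Define change in SAP 8.2.3 as the visit value minus the same patient's baseline, and name the baseline measurement for each table.
- In Tables 10 and 14 to 19, report at each time point the number of patients with both values, mean change, SD and 95% CI.
- For APTT, give the change in seconds. A within-patient percent change or ratio to baseline may be added, if defined.
- For temperature and the other vital signs, give absolute change only.
- Retitle Tables 14 to 19 as mean change from baseline.
- State how missing values and values taken after discontinuation are handled. The paired n shows the loss of patients but does not correct for it.
- Reconcile the synopsis stopping rules with Protocol 15.3 and 18.5.1 on whether they act on the patient or on the trial.
- Reconcile Tables 16 to 19, which need vital signs on Days 0, 1, 8 and 15, with the flow chart in Protocol 7.1, which marks them at screening only.

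The cost is SAP text, shells and programming. The exception is the follow-up vital signs: if they are not being collected, either the schedule or the tables must change.
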